### 6.0 Study Hypothesis

For subjects undergoing early RF ablation for recurrent, symptomatic PAF, it is hypothesized that, compared to the Drug Therapy (control) Group, the PVI (test) Group will demonstrate superior effectiveness as evidenced by a longer time needed to progress to persistent AF/AT during follow-up through 3 years.

### 7.0 Objective

The objective of this study is to determine whether in subjects with Paroxysmal AF (PAF), early RF ablation treatment using the THERMOCOOL® Catheter Family in conjunction with the CARTO® 3, CARTO® XP or CARTO® RMT System delays progression of AF compared with drug therapy (either rate or rhythm control) using current AF management guidelines.

## 8.0 Investigational Plan

### 8.1 Study Design

This is a prospective, multi-center, randomized (1:1), controlled, two-arm, open-label, clinical study, which will evaluate the effectiveness of early RF ablation intervention in delaying progression of PAF to persistent AF/AT, compared with drug therapy (either rate or rhythm control). Patients with recurrent, symptomatic PAF who meet the inclusion criteria will be considered for study participation and may be enrolled if no exclusion criteria apply.

### 8.2 Treatment Groups

Eligible subjects who sign the study informed consent form will be randomized into one of two treatment groups:

- **PVI (Test) Group:** RF ablation to achieve PVI using the THERMOCOOL® Catheter Family in conjunction with the CARTO® 3, CARTO® XP or CARTO® RMT System.
- **Drug Therapy (Control) Group:** AAD therapy in accordance with current AF management guidelines

The Test Group will be compared to the Control Group to determine differences with respect to various effectiveness and safety endpoints. Planned statistical analyses of endpoints and outcomes are described in Section 14 (Statistical Analysis) of this protocol.

### 8.3 Number of Centers

Up to 50 sites in Europe and/or the Asia Pacific, North-America region will participate in this study. Previous studies have reported cross-over rate ranges from 42% to 59% during the 1-year follow-up time; Santinelli *et al* study (2009) reports 87.9% cross-over rate during the four years follow-up time. To mitigate high cross-over rates and minimize the unilateral and random efflux from the Control Group, sites with the potential to minimize potential cross-over will be selected for study participation (refer to Section 9.2, Informed Consent and Enrolment Procedures, for additional detail). Total enrolment among all sites of up to 330 subjects is expected, with an approximately equal distribution between Test and Control Groups.

### 8.4 Study Duration, Completion, and Termination

- **Duration:** The study duration is anticipated to be 4-5 years; 1-2 years to complete screening/enrollment, and 3 years to complete follow-up for all subjects.
- **Completion:** The planned time of study completion is after all subjects have completed the required 3-year follow-up visits with the following exceptions: (a) subjects who withdraw from the study or who terminate early per protocol or investigator decision; and, (b) premature study stoppage for futility (see Termination).
- **Termination:** The study may be terminated prematurely at the discretion of the Sponsor or on statistical grounds (i.e., effectiveness or futility is determined). The Sponsor may also terminate a site prior to study completion if the Sponsor believes the site is no longer capable of participating (e.g., cannot fulfil subject enrolment goals, site suspension by EC / EB).

## 9.0 Subject Selection and Disposition

### 9.1 Recruitment and Screening Procedures

Patients who have failed at least 1 but no more than 2 prescribed drugs for AF (either anti-arrhythmic or rate control drug) will be screened for this study if eligible for both (i) RF ablation for treatment of recurrent, symptomatic PAF and (ii) medication management with either anti-arrhythmic or rate control drug. A screening log, maintained at each study site, will be used to document the subjects reviewed for potential enrolment into the study. The screening log should be completed for any patient considered for study inclusion, regardless of whether the patient is selected or not, as this will allow better management of the study enrolment rate.

### 9.2 Informed Consent and Enrolment Procedures

For this study, it is important to minimize the number of Control Group subjects who undergo RF ablation for AF, after cross-over, and thus confound the treatment group analyses. Because high cross-over rates from the drug treatment group to the ablation treatment group have been reported in studies similar to this one, the following measures will be implemented at each study site to minimize subject cross-over (refer to Appendix B for additional detail):

- Avoid recruiting/enrolling patients who are initially referred specifically for RF ablation.
- Select sites with:
  - Significant experience with RF ablation; and that also with a large AF patient population on medication management alone.
  - Commitment to enrolling subjects who do not show an obvious bias toward one treatment arm over another and who will agree to accept the treatment to which they are randomized.

The informed consent process will include a thorough discussion of the importance of minimizing cross-over in the Control Group (refer to Appendix B). Patients who exhibit a clear understanding of this and who are deemed eligible for and willing to participate in the study must sign (or have their legal representative sign on their behalf) the study's informed consent form (ICF), prior to enrolment and collection of any study-related data. The ICF and any revisions must have prior approval of the study site's ethics committee (EC) / ethics board (EB). The signed ICF will be kept in the subject's files.

### 9.3 Study Inclusion Criteria

1. Patients with recurrent paroxysmal AF for at least 2 years, with  $\geq 2$  episodes over the last 6 months;
2. HATCH Score of at least  $\geq 1$  and  $\leq 4$ .c
3. Eligible for catheter ablation and for anti-arrhythmic or rate control medications, after having failed at least 1 but no more than 2 prescribed drugs (either anti-arrhythmic or rate control drug).
4. Age 60 years or older.

---

c Hypertension (+1); Age >75 years (+1); previous TIA or Stroke (+2); COPD (+1); Heart failure - including systolic or diastolic heart failure (+2).

5. LA diameter  $\leq$  55mm by TTE.
6. LV ejection fraction  $\geq$  50% when in sinus rhythm or LV ejection fraction  $\geq$  35% when in AF.

NOTE: For patients entering the study in AF with an ejection fraction  $\geq$  35% and  $<$  50%; the ejection fraction should be re-checked when in sinus rhythm. In case the ejection fraction is  $\geq$  50% the subject can continue in the study.

7. Patient signed the Informed Consent Form and is able and willing to comply with protocol requirements, including all baseline and follow- up testing.

#### 9.4 Study Exclusion Criteria

1. Patients awaiting cardiac transplantation or other cardiac surgery.
2. Acute illness (ongoing) or active systemic infection or sepsis which in the opinion of the investigator, may adversely affect the safety and/or effectiveness of the participant of the study.
3. Reversible causes of AF, e.g. but not limited to thyroid disorders, acute alcohol intoxication, recent major surgical procedures or trauma,...
4. Recent cardiac events including MI, PCI, or valve or bypass surgery in the preceding 3 months.
5. Heart failure decompensation.
6. Previously diagnosed with persistent/permanent AF/AT
7. Previously required cardioversion  $>$ 48 hours after onset of AF/AT
8. Subject having previous TIA or stroke (cerebrovascular accident) one year prior to patient enrolment and/or no sufficient recovery.
9. Pulmonary embolism or recent atrial embolism/thrombosis.
10. Hypertrophic obstructive cardiomyopathy.
11. Class IV angina or Class IV CHF (including past or planned heart transplantation).
12. Mandated anti-arrhythmic drug therapy for disease conditions other than AF.
13. Heritable arrhythmias or increased risk for torsade de pointes with class I or III Drugs.
14. Prior LA catheter ablation with the intention of treating AF; prior surgical interventions for AF such as the MAZE procedure.
15. Prior AV nodal ablation.
16. Patients presenting contra-indications for the study catheter(s), as indicated in the respective Instructions For Use.
17. Contraindication to warfarin, other anticoagulation therapy, or all anti-platelet medications.
18. Medical conditions limiting expected survival to  $<$  3 years.
19. Concurrent participation in any other clinical study.
20. Prior history of non-adherence to prescribed drug regimens.
21. Women of child bearing potential whom are pregnant, lactating, or planning to become pregnant during the course of the trial

NOTE: Prior ablation of the cavo-tricuspid isthmus is not a reason to exclude, if the patient develops subsequent recurrent atrial fibrillation.

NOTE: For patients randomized to the PVI group (Test Group), a Transesophageal Echocardiography (TEE) should be performed (as per standard of care), within 48 hours pre-procedure, to exclude atrial thrombus or other structural contraindications for an ablation procedure.

## 9.5 Subject Disposition

- **Enrolled Subjects:** subjects who sign the study informed consent form and are randomized.
- **Excluded Subjects:**
  - **Test Group:** subjects who are enrolled and randomized to ablation therapy but never undergo insertion of the THERMOCOOL ablation catheter.
  - **Control Group:** subjects who are enrolled and randomized to medication management (AAD) but never begin taking investigator-prescribed AAD and are ineligible for ablation therapy.
- **Discontinued Subjects:**
  - **Test Group:** subjects who are enrolled and randomized to ablation therapy, undergo insertion of the THERMOCOOL ablation catheter, but do not undergo further ablation therapy (i.e., no RF energy is delivered). These subjects will be categorized as ‘discontinued’ if therapy is not possible due to equipment failure or if their arrhythmia is determined, at the time of electrophysiologic study, to be a non-study arrhythmia, e.g. atrial flutter, instead of PAF under investigation.
  - **Control Group:** subjects who are enrolled and randomized to medication management and have started an investigator-prescribed AAD, but do not complete the dose-loading period (~ 2 weeks), for reasons other than a safety failure or if their arrhythmia is determined to be a non-study arrhythmia, e.g. atrial flutter.
- **Lost to Follow-up Subjects:** All subjects should be encouraged to return for protocol required office, clinic visit for evaluation during the study follow-up period. If a subject is unable to return for an office or clinic visit or unable to be contacted by telephone, 3 separate telephone calls should be made to obtain subject related safety information. All attempts should be documented in the source documents. If the subject does not respond to the 3 telephone calls, then the investigator must send a certified letter to the subject. If the subject does not respond to the letter, then the subject will be considered “lost to follow-up” for the current study visit. Subject contact must be attempted at each follow-up time point and if unable to contact the subject after 3 phone calls, the subject should once again be sent a certified letter. Only after failing to contact the subject at the final follow-up visit, the subject will be considered lost to follow-up and the study termination/end form will be completed in the individual case report form.
- **Withdrawn / Early Termination Subjects:** investigator termination of a subject for reasons stated below in Section 9.6; or, subjects who withdraw consent for study participation and are terminated from the study prior to completion of all follow-up visits.
- **Completed Subjects:** enrolled subjects who have not been discontinued, withdrawn or lost-to-follow-up from the study, prior to the final 3-year study visit.

## 9.6 Subject Withdrawal

The investigator may remove a subject from the study for any of the following reasons: no longer meets eligibility criteria, withdrawal is in the subject’s best interest, subject preference, concurrent illness, noncompliance, or any other situation the investigator deems a compromise to the integrity of the study. Subjects will be informed prior to study entry that they are free to withdraw from the study at any time and for any reason, without prejudice to his or her future medical care by the physician or the institution. The Sponsor also has the right to withdraw a subject from the study at any time and for any reason.

If a subject is removed from the study, the date and reason for withdrawal will be recorded on the appropriate electronic case report form (eCRF). If the subject is withdrawn due to an adverse event (AE) or serious adverse event (SAE), the Investigator must comply with all reporting requirements and must follow the subject until the AE/SAE has resolved or stabilized.

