#### Health Economics (HE) Outcomes:

- Health care utilization (number and length of hospitalizations and unscheduled cardiovascular-related visits).
- Quality of Life (QoL) at 3 months, 6 months, 1 year, 2 years and 3 years by EQ-5D and AFEQT Questionnaire and change from baseline.

Note: AFEQT Questionnaire will only be used in validated languages and therefore, only distributed to a subgroup of the study population. The AFEQT questionnaire is validated in following languages:

French, German, Italian, Spanish (Spain), Spanish (US), Polish, Czech, Simplified Chinese (China), Traditional Chinese (Taiwan), Dutch, Korean, Norwegian, Swedish.

---

d Baseline presence of dementia would preclude subject enrolment in this study; however, new onset dementia could occur during the course of the study. If the dementia became sufficiently serious to preclude continued adherence to protocol requirements (Section 9.6), an Investigator may decide to terminate this subject from the study.

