### **11.2 Schedule of Examinations**

#### **11.2.1 Study Visits and Phone Follow-up**

Table 1 displays the required schedule for subject treatments and evaluations for Test and Control Groups. Sites participating in this study have been selected upon their capabilities to successfully carry out those assessments. Subjects will need to return to the hospital for a follow-up clinical visit at 3 months, 6 months, 1 year, 2 years and 3 years. Follow-up by phone will be conducted for all subjects at 9 months, 18 months and 30 months. Arrhythmia monitoring assessments, as described in Table 1, will be discontinued once subjects have progressed to persistent AF/AT.

All subjects will be followed through 3-years. Subjects who reach the primary endpoint (progress to persistent AF/AT) will only have to return for the final visit at 3 years; however, they will be followed for safety through the 3-years study period by their hospital and all adverse events are to be reported by the investigator as per protocol requirements. Subjects in the Test Group who undergo a repeat ablation procedure will continue follow-up according to the schedule of their index (first) ablation procedure. Thus, subject visits will be counted from the time of the index ablation procedure and not from the date of the repeat ablation procedure. Subjects in the Control Group who undergo an ablation procedure (cross-over), will continue follow-up according to their initial schedule.

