### **Transesophageal Echocardiography (TEE) – standard of care**

Transesophageal echocardiography must be performed for the Test Group within a 48-hour period immediately prior to the ablation procedure, to exclude atrial thrombus or other structural contraindications to an ablation procedure. Presence of a thrombus will require postponement of the ablation procedure or may even lead to exclusion of the subject from further study involvement. Copies of TEE reports should be filed in the subject's medical chart with the participating investigator.

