### 13.4 Sample Size and Power Calculation

A total sample size of 322 (161:161) subjects will be required to ensure 85% power to detect the effect size measured by negative log of the hazard ratio equal to 1.154f (treatment group over control group). This calculation assumes a 50% cross-over rate from the AAD group to the ablation group, a 10% drop-out rate in each group over the 3 year follow-up period, and 1.5 years accrual time. This calculation is based upon one-sided superiority testing with alpha equal to 0.025. Using meta-analysis, the rates of disease progression at the end of follow-up are estimated to be 25% and 5% in the AAD and ablation group, respectively (see the point estimate justification document for details, Appendix C). The sample size calculation is based upon the method developed by Rubinstein, Gail and Santner (RGS,1981) and also incorporates group sequential design with multiple interim looks.

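### Removal for lost eligibility, or after a Test-only TEE finding, may cause informative censoring of the primary endpoint that no planned analysis examines

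*Protocol*

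**What the plan says.** Protocol 9.6: "The investigator may remove a subject from the study for any of the following reasons: no longer meets eligibility criteria". Follow-up after removal is required there only when the subject leaves because of an AE or SAE, and then until that event settles. Nothing is said about collecting the primary endpoint.

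The eligibility limits (Protocol 9.3 and 9.4) include LA diameter of at most 55 mm, HATCH of at most 4, an LVEF floor and no decompensated heart failure. Protocol 10.2 and 13.12.4 re-measure LA size, HATCH and NYHA class as conditions possibly linked to progression.

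Three other places bear on leaving the study:

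- The TEE paragraph of Protocol 11.2.1, which applies to the Test Group only, says that a thrombus "may even lead to exclusion of the subject from further study involvement".
- Protocol 9.5 classes a Test subject who receives no RF energy as discontinued "if their arrhythmia is determined, at the time of electrophysiologic study, to be a non-study arrhythmia". Control has a matching non-study-arrhythmia ground, without an EP study.
- Footnote d to Protocol 10.2 says that, if new dementia prevents adherence, "an Investigator may decide to terminate this subject from the study".

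Against these, Protocol 11.2.1 says "All subjects will be followed through 3-years". Protocol 8.4 excepts subjects who end early under the protocol or by investigator decision.

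On analysis, Protocol 13.6 and SAP 7 keep withdrawn subjects in the ITT set. SAP 8.3 censors subjects without an event at the later of the last visit and the last TTM. SAP 8.2 drops multiple imputation for the ITT population, arguing that the log-rank test handles censoring whatever its cause.

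**The concern.** A log-rank comparison is valid under censoring only if, within each arm, censored subjects carry the same later risk as those still followed. Removal because a progression-related limit has been crossed can break that condition. In an open-label trial the decision is also made by someone who knows the arm. For example, new heart failure adds 2 HATCH points and takes a subject from 3 to 5, past the limit. Protocol 5.1 cites a study with 25–40% annual progression at HATCH 2–7 against below 10% at 0–1.

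Stopping an assigned treatment does not require stopping endpoint follow-up, but the plan does not separate the two. With 28 planned events, a modest selective loss in one arm could move the type I error or the power. The analysis of new-onset progression factors would also lose the subjects it needs.

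**Working it through.** **The plan's own figures.** Protocol 13.4 gives: "A total sample size of 322 (161:161) subjects will be required to ensure 85% power to detect the effect size", with "negative log of the hazard ratio equal to 1.154". It adds: "This calculation is based upon one-sided superiority testing with alpha equal to 0.025". The Control rate after cross-over is 0.5 × 25% + 0.5 × 5% = 15%, and the Test rate is 5%.

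- Effect size: −ln[ln(0.95)/ln(0.85)] = 1.1532 (printed as 1.154; the difference is immaterial). HR = 0.316.
- Events (Schoenfeld): 4(1.960 + 1.036)²/1.1532² = 27.0, rounded up to 28. This equals the final look in Protocol Table 6.
- Sample size: two proportions, 15% against 5%, one-sided 0.025 and 85% power give 161 per arm, or 322.

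The design figures reproduce. The point is about follow-up, not arithmetic.

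**The path to censoring.** HATCH is re-scored at every clinic visit and TTE is repeated at years 1, 2 and 3 (Protocol Table 1), so a crossed limit can be seen. Protocol 9.6 then permits removal. No endpoint collection is required afterwards, SAP 8.3 censors the subject, and SAP 8.2 removes the one planned check. The HRS 2017 and per-protocol analyses (SAP 10.2 and 10.5) censor in the same way, so neither tests the assumption.

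**Size, closed form.** Suppose a fraction f of Test only is removed before any event, with risk RR times the arm average, and the true HR is 1. The apparent HR is (1 − f·RR)/(1 − f). With 28 events, one-sided alpha is 1 − Φ(1.96 + √(28/4) × ln HR).

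- f = 3%, RR = 3: HR = 0.91/0.97 = 0.938, alpha 0.037.
- f = 5%, RR = 3: HR = 0.85/0.95 = 0.895, alpha 0.048.
- f = 5%, RR = 5: HR = 0.75/0.95 = 0.789, alpha 0.091.
- RR = 1: HR = 1, alpha 0.025 for any f.

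**Size, simulation.** Log-rank test with 161 per arm, 3 years, 10% drop-out and critical value 1.96. A 10% stratum has RR times the hazard of the rest of the arm, and 30% or 50% of it is removed before any event (3% or 5% of the arm, about 5–8 subjects). Alpha uses 10% progression in both arms; power uses 15% against 5%.

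| Removal | RR | Alpha | Power |
|---|---|---|---|
| None | 3 | 0.023 | 84% |
| Test only, 3% | 3 | 0.032 | 85% |
| Test only, 5% | 3 | 0.042 | 86% |
| Test only, 3% | 5 | 0.038 | 84% |
| Test only, 5% | 5 | 0.055 | 86% |
| Control only, 5% | 3 | 0.017 | 75% |
| Control only, 5% | 5 | 0.011 | 68% |
| Both arms, 5% each | 3 | 0.025 | 81% |

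Alpha rests on 8,000 runs per row and power on 4,000, so the standard error is about 0.002 on alpha and 0.6 points on power. The 0.023 and 0.025 are not distinguishable.

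The two methods agree once RR is on one scale. RR 3 against the rest is 3/(0.9 + 0.3) = 2.5 times the arm average, and RR 5 is 5/(0.9 + 0.5) = 3.57 times. At f = 5% the closed form then gives alpha 0.041 and 0.058, against 0.042 and 0.055 simulated. The simulated range is used below.

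**The case against.** The 9.6 rule is permissive, and other text expects worsening subjects to stay. Protocol 13.12.4 models increases in LA size and HATCH over all follow-up assessments. Follow-up TTE is only annual, so removal shortly before an event on LA grounds is not something the schedule makes likely. Protocol 8.4 already excepts early termination. The reason for each removal is recorded (9.6) and summarised by arm (Protocol 13.7, SAP 9.1), so imbalance would be visible. All of this stands. It shows that the passages conflict and that loss is possible rather than demonstrated. Visible imbalance is still not analysed.

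Three stronger readings are tempting, and the documents do not support them.

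- *The ITT set loses these subjects.* It does not. They are kept and censored.
- *The Test arm is made healthier.* This is not shown. Section 9.6 and footnote d apply to both arms, and Control has its own non-study-arrhythmia ground; only detection by EP study is specific to Test. Thrombus is not among the progression factors listed in Protocol 10.2. The example of a non-study arrhythmia is atrial flutter, and the endpoint excludes the isthmus-dependent form. The TEE text puts postponement first and exclusion as a further possibility.
- *A handful of removals decides the trial.* With Z = (D/2 − T)/√(D/4), where D is total events and T is Test events, 7 Test events of 28 give 2.65 and 10 of 31 give 1.98, against the final bound of 2.0507. But losing three events takes three removals only if each subject was certain to progress. At the planned 5% Test rate, threefold risk is 15%, so 3/0.15 = 20 removals are needed; fivefold risk needs 3/0.25 = 12. The planned 10% drop-out is about 16 per arm in total.

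**Conclusion.** The concern holds as a risk of informative censoring that the plan allows and does not test. It is not a demonstrated bias. Size and direction are undetermined: loss in Test favours ablation, and loss in Control works against it.

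If 3–5% of Test only were lost selectively at relative risk 3–5, one-sided alpha would rise from about 0.023 to about 0.03–0.055. If about 5% of Control only were lost, power would fall from about 84% to 68–75%. Equal loss in both arms at relative risk 3 would leave alpha unchanged and cost about 3 power points. The removal fractions, relative risks and confinement to one arm are all assumptions; the documents give none of them. Subjects who reach persistent AF/AT before removal count as events and are unaffected.

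The change is worth making because it is cheap and the trial rests on few events.

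**What to change.** **Protocol**

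- 9.6: delete loss of eligibility as a ground for leaving the study, and state that eligibility applies at randomization.
- 9.5 and the TEE paragraph of 11.2.1: state that subjects who are not ablated, or who stop assigned treatment, stay on the existing visit and TTM schedule for the endpoint to 3 years unless they withdraw consent, die or are lost to follow-up.
- Reconcile this with 8.4, the 3-year follow-up statement in 11.2.1, and footnote d. Decisions about the procedure and drugs are unchanged.

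**SAP**

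SAP 5.1 says that the study ended early, so new protocol wording cannot recover follow-up already lost. The SAP can still:

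- tabulate investigator and sponsor removals by randomized arm and specific reason, including the 9.6 ground and any TEE or EP-study finding, with time of removal;
- restore an ITT sensitivity analysis for informative censoring, such as the multiple imputation planned in Protocol 13.10, with a raised event risk for removed subjects varied by arm;
- give a start date for Test subjects never ablated. SAP 8.3 starts the Test clock at the procedure, so their follow-up has no time origin.

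**Cost:** a small amount of extra follow-up on visits and TTM that already exist, plus one table and one sensitivity analysis.
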